### Missing or Incomplete Dates for Adverse Events and Concomitant Medications

Imputation of Start and End Dates of Adverse Events and Concomitant Medications

The following rules will be used where applicable to impute partial or completely missing start dates or end dates:

- If only the day is missing for a start date, the 1st of the month will be imputed. If the new estimated date falls before the date of first dose, while the known month and year match the month and year of the first dose, the date of first dose will be used as the new estimated date. For AEs, the AE will be considered as a TEAE.
- If only the day is missing for an end date, the last day of the month will be imputed. If the new estimated date falls after the date of last study visit, the date of last study visit will be used as the new estimated date.
- If both the day and the month are missing for a start date or end date, no imputation will be used, and the duration will not be calculated. For an AE, if the year of start is the same or greater than the year of the first dose date, the AE will be considered as treatment emergent.
- If the start date or end date is completely missing, duration will not be calculated. However, an event with completely missing start date will be considered as treatment emergent.

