### **Standard Calculations**

Variables requiring calculation will be derived using the following formulas:

• **Days** – A duration expressed in days between 1 date (date1) and another later date (date2) will be calculated using the following formula:

Duration in days = date2 - date1 + 1

• **Body mass index (BMI)** – BMI will be calculated using height (cm) and weight (kg) using the following formula:

BMI  $(kg/m^2)$  = weight  $(kg)/[[height (cm)/100]^2]$ .

• Change from baseline – Change from baseline will be calculated as:

Change = post-baseline value – baseline value.

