### 10.3 Prior and Concomitant Medications

Prior and concomitant medication verbatim terms in the eCRFs will be mapped to anatomical/therapeutic/chemical class and preferred names using the WHODrug Global B3 (version 01MAR2019).

• Prior medications are defined as medications with a stop date before the date of the first dose of study drug.

Concomitant medication are medications with a start date on or after the date of first dose of study drug administration or are medications started before study drug administration and ended after study drug administration.

Prior and concomitant medications will be summarized by WHO ATC class and preferred name. These summaries will present the number and percentage of subjects using each medication. Subjects may have more than 1 medication per ATC class and preferred name. At each level of subject summarization, a subject is counted once if he/she reported 1 or more medications at that level. Each summary will be ordered by descending order of incidence of ATC class and preferred name within each ATC class.

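### SAP Section 6 ignores a known end date when an adverse event's start date is partial or missing, so an event that ended before the first dose can be counted as treatment-emergent

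*SAP*

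**What the plan says.** The rules are in SAP Section 6, under Missing or Incomplete Dates for Adverse Events and Concomitant Medications. There are three cases for the start date.

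- **Day missing.** "If only the day is missing for a start date, the 1 st of the month will be imputed". If that puts the start before the first dose although the recorded month and year match first dosing, the rule reads: "the date of first dose will be used as the new estimated date. For AEs, the AE will be considered as a TEAE".
- **Day and month missing.** "no imputation will be used, and the duration will not be calculated". For an adverse event the year alone decides: "if the year of start is the same or greater than the year of the first dose date, the AE will be considered as treatment"; that is, it counts as treatment-emergent.
- **Completely missing.** No duration is computed, and "an event with completely missing start date will be considered as treatment emergent".

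None of the three carries a condition on the end date, and nothing elsewhere in the SAP adds one. Standard Calculations, in the same section, gives "Duration in days = date2 - date1 + 1", where date2 is the later of the two dates.

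Medications are classified separately, in SAP 10.3. "Prior medications are defined as medications with a stop date before the date of the first dose of study drug". The concomitant class covers "medications with a start date on or after the date of first dose of study drug administration or are medications started before study drug administration", the second group only if use continued past dosing. The SAP does not say that the two classes exclude each other, or which prevails if a record meets both.

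**The concern.** Treating an event as treatment-emergent when its onset is uncertain is a sound convention. The uncertainty disappears when a complete end date shows that the event was over before the first application. Counting it then contradicts three definitions:

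- Protocol 8.1.2 requires the event to follow the first application.
- Protocol 10.4.2 limits the adverse event summaries to events after the first dose.
- SAP 10.4 requires onset on or after the first dosing date, or worsening of an existing event.

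Such records can arise. Protocol 6.3.1 and 8.3.1 collect adverse events from consent, and Screening may start up to 34 days before Day 1. Adverse event frequency and severity is a primary endpoint (Protocol Section 2, SAP 3.1), and with about 20 subjects a single event is visible in a table.

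Programming checks would not catch the problem. SAP Appendix B requires two independently programmed datasets to agree, and two programmers who follow the text will make the same error. Listings show the dates as recorded, so the end date in the listing could contradict the treatment-emergent table.

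**Working it through.** The plan states no figure to reproduce. The check applies its rules to records whose end date is known and precedes the first dose. The calendar dates are illustrative assumptions: first dose 20 August 2019, recorded end 10 August 2019.

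**Inputs.** The start-date rules and the duration formula are from SAP Section 6, the medication definitions from SAP 10.3, and the sample size of about 20 from Protocol 4.1.

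**Results by type of start date**

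| Recorded start | Imputed start | Duration (days) | Adverse event counted as treatment-emergent | Medication class |
|---|---|---|---|---|
| Aug 2019, day missing | 20 Aug 2019 | 10 − 20 + 1 = −9 | Yes | Prior and concomitant |
| Jul 2019, day missing | 1 Jul 2019 | 41 | No | Prior only |
| 2019 only | None | None | Yes | Prior only |
| 2018 only | None | None | No | Prior only |
| Completely missing | None | None | Yes | Prior only |

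The treatment-emergent error therefore occurs in all three rules (for year-only starts, when the year is the first-dose year or later). The reversed dates and the double medication label occur in the first row only.

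**Whether the first row depends on the dates chosen.** In a 31-day month, let the first dose fall on day k (2 to 31) and the end on day e < k.

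- Number of combinations: 1 + 2 + … + 30 = 30 × 31 / 2 = 465.
- The imputed start is day k, which is later than e in all 465, and all 465 are counted as treatment-emergent.
- Duration is e − k + 1. It is lowest at e = 1, k = 31 (1 − 31 + 1 = −29) and highest at e = k − 1 (0). It is never positive.

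**Size.** One subject in 20 is 1/20 = 5 percentage points of a term's incidence. This is an upper bound per subject, because SAP 10.4 counts a subject once per term. A subject who also has a genuine treatment-emergent event of the same term adds nothing.

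**The first row with an end-date check.** The end precedes the first dose, so the start stays at 1 August 2019. Duration is 10 − 1 + 1 = 10 days, the event is not treatment-emergent, and the medication is prior only.

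**The case against.** The case for leaving the text alone has several parts.

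- **Direction and use.** The error can only over-count treatment-emergent events, which is the cautious direction, in a single-arm study with no formal comparison of safety data. This limits the consequence, but it does not justify counting an event that the data show to be pre-treatment.
- **Rarity.** An incomplete start date must coincide with a known end before the first dose. Adverse events are reviewed at Screening, Day -1 and Day 1, and Protocol Section 9 has inconsistent data queried. This stands. Early collection of events and medications might suggest that affected records are common, but the documents give no frequency.
- **Durations.** The formula is written for an earlier and a later date, and SAP 10.4 and Appendix C plan no table of event or medication duration. This also stands. The negative value shows that the imputed date is impossible; it would not be a reported result.
- **Medications.** A reader might infer that medications, like events, are classified from the start date alone. They are not, because SAP 10.3 defines prior use by the stop date. The defect is a double label in one case, which would place the record in both Table 14.1.5.1 and Table 14.1.5.2.
- **Washed-out drugs.** A reader might also infer that prohibited drugs stopped before entry would appear as on-study use. For an eligible subject this is close to impossible. The drug must have started in the first-dose month and stopped at least 2 weeks (topicals) or 4 weeks (systemic treatments) before Baseline. That requires a first dose on about the 15th or later, or about the 29th or later. Named biologics need 4 weeks to 12 months. A drug started in an earlier month is prior only.

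**Conclusion.** The point holds for adverse events. All three start-date rules can make an event treatment-emergent although its recorded end precedes the first dose, against the protocol's definition and the SAP's own. This is a stated rule that gives a wrong answer, not a missing detail.

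Two side effects are confined to a day-missing start in the first-dose month: an imputed start later than the known end, and a medication that is both prior and concomitant. It would be wrong to extend either to the other two rules, which impute no start date and compute no duration.

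The practical weight is small. The ceiling is 5 percentage points per affected subject and term, assuming about 20 subjects in the safety analysis set. The number of affected subjects is unknown and probably low. The case for acting is that the endpoint is primary and the correction is almost free.

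**What to change.** Add a condition to the start-date rules in SAP Section 6 and a precedence statement to SAP 10.3:

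- Use the first-dose date as the imputed start, and apply the treatment-emergent defaults, only when the end date is missing, the record is ongoing, or the end could be on or after the first dose. For a partial end date, judge this by the latest date that the recorded part allows.
- Otherwise, classify the adverse event as not treatment-emergent. Under the day-missing rule keep the first-of-month start; under the other two rules continue to impute none.
- State that a medication with a stop date before the first dose is prior only.

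The cost is a sentence or two in the SAP and one condition in the dataset program. The conservative default remains wherever the timing is truly unknown, and no data collection changes.

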### **Standard Calculations**

Variables requiring calculation will be derived using the following formulas:

• **Days** – A duration expressed in days between 1 date (date1) and another later date (date2) will be calculated using the following formula:

Duration in days = date2 - date1 + 1

• **Body mass index (BMI)** – BMI will be calculated using height (cm) and weight (kg) using the following formula:

BMI  $(kg/m^2)$  = weight  $(kg)/[[height (cm)/100]^2]$ .

• Change from baseline – Change from baseline will be calculated as:

Change = post-baseline value – baseline value.

### 7. ANALYSIS SETS

### Safety Analysis Set

All subjects who receive at least 1 application of study drug will be included in the safety analysis set. Subjects will be analyzed as treated.

### **PK Analysis Set**

All subjects who have at least 1 application of study drug and have at least 1 evaluable PK assay result will be included in the PK analysis set. A value that is below the limit of quantification is considered evaluable.

### QT/QTc Analysis Set

The QT/QTc analysis set will include all subjects in the safety analysis set with measurements at Baseline as well as on-treatment with at least 1 post-dose time point with a valid  $\Delta$ QTcF value.

### PK/QTc Analysis Set

The PK/QTc analysis set will include all subjects who are in both the QT/QTc and PK analysis sets with at least 1 pair of post-dose PK and QTcF data from the same time point.

### 8. STUDY POPULATION

### 8.1 Subject Disposition

Subject disposition information will be summarized using the safety analysis set. The summary will include: the number of subjects in each analysis set, the number of subjects completing the study, and the primary reason for discontinuation.

### **8.2** Protocol Deviations

Major protocol deviations that could potentially affect the efficacy or safety conclusions of the study will be identified prior to database lock.

A listing of all protocol deviations including the deviation designation (major or minor) and deviation category will be presented in a data listing.

### 8.3 Eligibility

A listing of subjects not fulfilling any eligibility criteria will be created.

### 8.4 Demographic and Baseline Characteristics

Demographic variables include age, sex, ethnicity, race, height, weight, and body mass index (BMI). Age will be calculated in years relative to the informed consent date. Baseline characteristics include physician global assessment (PGA), percent body surface area affected (%BSA), and psoriasis area and severity index (PASI) score.

Demographic and baseline characteristics as well as medical history will be summarized using the safety analysis set. In addition, demographic and baseline characteristics as well as medical history will be listed by subject.

### 9. EFFICACY ANALYSES

All efficacy analyses will be performed based on the safety analysis set. The secondary study endpoints include mean change from Baseline at Day 29 in PGA, %BSA, and PASI. Descriptions of these endpoints can be found in Protocol Appendix 1 and 2.

The PGA, %BSA, and PASI will be summarized using descriptive statistics at Baseline and Day 29. Change and percent change from Baseline to Day 29 will be summarized descriptively including 95% confidence intervals and analyzed with a one sample t-test.

The one sample t-test will test the following hypotheses:

- $H_0$ : The mean change or percent change from baseline to day 29 in efficacy endpoint is equal to 0;
- H1: The mean change or percent change from baseline to day 29 in efficacy endpoint is not equal to 0;

### SAS code examples:

```
proc ttest data=DATAset sides=2 alpha=0.05 h0=0;
    var CHG;    *PCHG-for Percentage Change*;
run;
```

CHG = Change from Baseline to Day 29. PCHG = Percentage change from Baseline to Day 29.

In addition to the above, the percent of subjects with treatment success at Day 29 will be summarized. Treatment success is defined as at least a 2-grade improvement from Baseline in PGA as well as a PGA score of clear or almost clear (score of 0 or 1) at Day 29. Percent of subjects with 1-point improvement and percent of subjects with 2-point improvement from Baseline at Day 29 will also be summarized.

In addition, Physician Global Assessment (PGA), Percent Body Surface Area (%BSA) Assessment and Psoriasis Area and Severity Index (PASI) Assessment will be listed by subject.

### 10. SAFETY ANALYSES

The safety analysis set will be used in the analysis of safety and biomarker data. Data will be listed by subject and summarized. No formal statistical comparisons will be made for safety data. Unless otherwise noted, baseline is defined as the last non-missing value recorded prior to the first dose of study drug.

### 10.1 Interim Analysis and Data Monitoring

There are no planned interim analyses for this study. The Sponsor may review PK data in an ongoing basis during the study.

### 10.2 Extent of Exposure and Measurement of Treatment Compliance

[figure not shown]
The extent of exposure to study drug will be summarized by the number of applications, number of missed applications and compliance with study treatment. A subject will be considered compliant with the dosing regimen if the subject applied 80% to 120% of the total number of expected doses during the treatment period. The expected number of doses during the treatment period is 29.

Dosing information will be presented in listings and will include the tube dispense and return weights as well as dates and time of study drug administration.

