5.4. Compliance with Study Drug Administration

At Baseline, study staff will provide the subject with detailed instructions concerning protocol requirements and use of study drug. Additionally, subjects will be asked to complete a daily diary with the time of each application of study drug. At each post-Baseline study visit, study staff will review use of study drug, as applicable, with the subject.

When subjects are dosed at the site, they will apply the study drug under supervision of the study staff. The date and time of each dose administered in the clinic will be recorded in the source documents. The study drug and study subject identification will be confirmed at the time of dosing by a member of the study site staff other than the person dispensing the study drug.

At the time of dispensing study drug to each subject, site personnel will weigh the tubes to be dispensed and will record the weight of all tubes dispensed at each visit in the drug accountability log. Subjects will be instructed to bring all used and unused tubes of study drug with them to each study visit. Site personnel will weigh returned tubes (used and unused) and record the combined tube weight in drug accountability log. If a tube has been lost, discarded, or forgotten by the subject, then the site personnel will make a notation of this on the drug accountability log. The site personnel will remind the subject to keep all tubes of study drug dispensed and to bring all used and unused tubes to each clinic visit. These data will be used to estimate subject compliance with use of study drug. Tubes of study drug dispensed at the most recent prior visit which remain unopened (the foil cap on the tube remains fully intact/undisturbed) may be re-dispensed to study subjects at the current visit. Opened, partially used tubes or tubes with foil overlay removed are not to be re-dispensed to study subjects. If there is any question as to re-dispensation, sites should issue new tubes of study drug to the subject(s).

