6.4. Treatment of Study Drug Overdose

For this study, accidental or intentional oral ingestion of study drug or excessive application onto the skin (e.g., using a greater quantity, or applying more frequently than instructed) will be considered an overdose. Ingestion of a 30 gram tube of tapinarof cream, 1% would result in an oral dose of 300 mg.

The Sponsor does not recommend specific treatment for an overdose; however, in the event of an overdose, the Investigator (or treating physician) should do the following:

- Contact Medical Monitor to discuss the event;
- In the event of excessive topical application, instruct the subject to wash study drug off of the skin and monitor for application-site AEs;
- Closely monitor the subject for AEs/SAEs and laboratory abnormalities;
- Provide general symptomatic treatment as necessary;
- Document the quantity of the excess dose as well as the duration of the overdosing in the eCRF;
- If the Medical Monitor requests a plasma sample for PK analysis, then a blood sample for PK should be obtained within 2 days from the date of the last dose of study drug.

Decisions regarding dose interruptions or modifications following an overdose will be made by the Investigator in consultation with the Medical Monitor based on the clinical evaluation of the subject.

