Study drug application instructions will be reviewed at all post-baseline clinic visits. On clinic visit days, subjects will be instructed/reminded on how to apply study drug (except during the final treatment/end-of-study visits). During the clinic visits, subjects will apply the daily dose of study drug while on-site under the supervision of site personnel, after other assessments have been completed.

Subjects who withdraw from the study before Day 30 will complete an Early Termination Visit. Study duration for subjects who complete this study is approximately 10 weeks in total. Refer to the study protocol for further details (Section 6 for descriptions of study procedures and assessments and Section 7 and the Schedule of Assessments [Table 1] for timing of procedures and assessments).

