### **Treatment Groups and Duration**

All subjects will receive tapinar of cream, 1% for 29 days with once daily application.

A subject will be considered to have completed the study when he/she completes all required procedures/visits for the 29-day treatment phase.

[figure not shown]

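### SAP 10.2 measures compliance only as applications out of a fixed 29, so amount applied is never summarised and some early stoppers and some extra applications are mislabelled

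*SAP*

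**What the plan says.** SAP 10.2 summarises exposure by number of applications, number of missed applications and compliance. A subject is compliant if he or she "applied 80% to 120% of the total number of expected doses" in the treatment period, and "The expected number of doses during the treatment period is 29". No other denominator is given for a subject who stops early, although SAP section 4 foresees this: "Subjects who withdraw from the study before Day 30 will complete an Early Termination Visit". Tube dispense and return weights go into listings. SAP section 12 repeats the application-count rule among the changes to protocol-specified analyses and does not mention the weights.

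Protocol 5.4 has site staff weigh tubes when they are dispensed and returned, and note any that are lost, discarded or forgotten. It then says: "These data will be used to estimate subject compliance with use of study drug". Home application times come from the daily diary.

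Protocol 6.4 covers excessive skin application, by quantity or by frequency, and states no tolerance: "applying more frequently than instructed) will be considered an overdose".

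**The concern.** Protocol 1.1.2 gives the purpose of a maximal-use study as measuring systemic exposure under conditions that maximise absorption, with the results intended to support US registration. How much cream went on the skin is therefore part of interpreting the PK results. The protocol collects the data for this and commits to using them for compliance. The SAP replaces that with a pure count and does not record the replacement as a change. SAP section 11 normalises Cmax and AUC to diseased area, not to amount applied, so the gap is not filled elsewhere.

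The count itself has two weak points. A fixed denominator of 29 mixes stopping early with skipping doses. An upper limit above 100% gives the label compliant to a pattern that the protocol defines as an overdose.

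**Working it through.** **Inputs.** Once-daily application for 29 days (SAP, Treatment Groups and Duration); 29 expected doses and the 80% to 120% band (SAP 10.2); about 20 subjects (Protocol 4.1).

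**The plan's own figure.** Once daily from Day 1 to Day 29 inclusive: 29 − 1 + 1 = 29. This is correct for a completer.

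**The band in whole applications.** 0.80 × 29 = 23.2 and 1.20 × 29 = 34.8, so 24 to 34 applications count as compliant.

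| Applications | Percent of 29 | Label |
|---|---|---|
| 23 | 79.3% | non-compliant |
| 24 | 82.8% | compliant |
| 28 | 96.6% | compliant |
| 30 | 103.4% | compliant |
| 34 | 117.2% | compliant |
| 35 | 120.7% | non-compliant |

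**(a) Amount applied.** No weight enters the formula. Any subject with one application a day for 29 days scores 29/29 = 100%, whatever quantity was used each time. In SAP Appendix C, exposure and compliance share one table, 14.3.1, whose content is set by SAP 10.2. Weights appear only in listings (SAP 10.2; dispensing and collection are Listing 16.2.5.2).

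**(b) Early stopping with no missed dose.** The count equals the day of the last dose.
- Last dose on Days 1 to 23: at most 23/29 = 79.3%, non-compliant. Hypothetical examples are Day 10, 10/29 = 34.5%, and Day 15, 15/29 = 51.7%.
- Last dose on Days 24 to 28: 82.8% to 96.6%, compliant.
- For comparison, a completer who missed five doses has 24/29 = 82.8% and is compliant.

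Counted to the subject's own last day on treatment, the adherent early stopper scores 10/10 or 15/15 = 100%.

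**(c) Extra applications.** Over 29 days, 30 to 34 applications (1 to 5 extra) are labelled compliant; 35 or more are not. The fixed denominator can also hide a higher frequency. Twice-daily use for 14 days followed by withdrawal gives 28/29 = 96.6%, compliant; against the subject's own 14 days it is 28/14 = 200%. The same masking occurs for 12 to 17 days of twice-daily use (24 to 34 applications).

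A subject-specific denominator alone does not settle (a), and it does not flag 30 to 34 applications in a completer.

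**Size.** One subject in 20 is 1/20 = 5 percentage points of the reported rate. The documents give no expected withdrawal or overdose rate, so the number affected cannot be calculated.

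**The case against.** The strongest case for the plan has four parts.

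*Measuring against the planned 29 doses is legitimate.* It captures persistence, whereas a denominator that ends at discontinuation scores a subject who stops on Day 3 as 100%. SAP 10.2 also reports applications and missed applications, and SAP 8.1 reports completion and reasons for discontinuation, so early stopping can be separated from skipped doses. This largely stands. It is why the second denominator should be added, not substituted.

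*Compliance is not the overdose detector.* Protocol 6.4 has its own route: contact with the Medical Monitor, monitoring, and eCRF documentation of the excess and its duration. Dosing dates and times are also listed. This stands too. A reader might infer that overdoses would go unrecorded or that any overdosing passes as compliant; the documents support neither. What remains is the conflict of labels at 30 to 34 applications.

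*The weights are not discarded.* A reader might infer that the SAP ignores them, but it commits to listing them. Nor does Protocol 5.4 prescribe grams per application or any other statistic, and the protocol sets no target quantity beyond a thin layer. Grams used therefore cannot give a compliance threshold. The protocol's stated use is still unmet and its omission unrecorded.

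*Key doses are supervised.* Protocol Table 1 has in-clinic application on Days 1, 2, 15 and 29, which covers the PK-profile doses. That leaves 29 − 4 = 25 scheduled applications at home, and for in-clinic doses Protocol 5.4 asks for date and time, not quantity.

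**Conclusion.** The point holds as a cheap improvement to a descriptive table. Its firmest part is (a): the protocol says the weight data will be used to estimate compliance, the SAP only lists them, and SAP section 12 does not say the use was dropped. Parts (b) and (c) hold within limits: no missed dose and a last dose on or before Day 23, and 30 to 34 applications over 29 days.

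A reader might infer that every adherent early withdrawal is mislabelled. That is not so, because last doses on Days 24 to 28 pass. A reader might also infer that the PK, efficacy or safety results are affected. No analysis set in SAP section 7 is defined by compliance, so they are not; what suffers is how well the exposure table describes use of the cream.

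The arithmetic assumes that the band is applied to whole applications without rounding, and that 29 is used for every subject because no other rule is given. The early-stopping and extra-application cases are hypothetical.

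**What to change.** In SAP 10.2 and Table 14.3.1:

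1. Summarise grams used, in total and per recorded application, from dispense and return weights. Report the number of subjects with lost or unreturned tubes. Present this as a descriptive exposure measure, since the protocol sets no target amount.
2. Keep the planned 29-dose compliance row and add one with expected doses counted up to the subject's own discontinuation.
3. Reconcile the upper limit of the band with Protocol 6.4, and report days with more than one application separately.

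The cost is SAP wording and a few table rows. Tube weights and application times are already collected. Gram totals will be imprecise where tubes are missing.
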